1. SYNOPSIS

Primary Study Objective	To compare gene expression stimulated by a semi-permanent filler and a biostimulator via punch biopsy
Secondary Study Objective	To assess and compare volume change in the nasolabial fold via clinical photography
Methodology	Randomized, single-center, comparative study
Number of Subjects	20 subjects to complete (10 subjects per treatment product group)
Study duration	13 weeks total
Study treatment products	Sculptra® - poly L-lactic acid (PLLA) biostimulator Radiesse® (+) – calcium hydroxylapatite (CaHA) semi-permanent filler
Conditions of use	Per on-label instruction
Study visits	Visit 1 (Day 0/baseline), visit 2 (day 5), visit 3 (day 28/week 4), visit 4 (day 84/week 12), and visit 5 (day 89).
Specific Inclusion Criteria:	
 ○ Demographics and study skin conditions 
 - Any race and ethnicity (to be recorded) - Fitzpatrick skin type (to be recorded) - Women or men - Age: 22-50 years old - Subject with a minimum of shallow nasolabial fold (NLF) contour deficiencies as assessed via the wrinkle assessment scale (WAS) - Subject with identical WAS scores on both NLFs - Subject who in the opinion of the treating Investigator would only need 2 treatments for optimal clinical outcomes - Subject with healthy immune systems ○ Administrative 
 - Ability of giving consent for participation in the study - Agreement to have skin biopsies on NLFs

	
 - Agreement to adhere to the procedures and requirements of the study and to report to the institute on the day(s) and at the time(s) scheduled for the assessments

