5. STUDY OBJECTIVES AND CLINICAL HYPOTHESIS

5.1 Study Objectives

The primary objective of this study is to compare gene expression stimulated by a semi-permanent filler and a biostimulator via punch biopsy.

The secondary objective of this study is to assess and compare volume change in the NLF via clinical photography.

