6. SELECTION AND DISPOSITION OF STUDY POPULATION

6.1 Number of Subjects

An appropriate number of subjects meeting inclusion/exclusion criteria listed below will be enrolled on the study to achieve maximum 20 subjects who complete the study as planned.

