7.6 Treatment Dosage and Mode of Administration

The injection technique (skin disinfection material, type of syringe, type and gauge of the intradermal needle, penetration angle, depth) will be the technique customarily used by the Investigator. The type of gauge of the injection needle will be recorded in the CRFs.

PLLA: two treatment sessions at 4-week interval with the first treatment at Visit 1 and the second treatment at Visit 3. Each treatment session will be consisted of multiple deep dermal injections, up to 9 mL/session (or up to 4.5 mL/NLF/session), into the left and right NLFs of each subject according to the IFU. The treatment amount for each PLLA subject will be determined at the Investigator discretion to achieve an optimal correction. Within each PLLA subject, the amount of each treatment needs to be equal at the left and right NLFs because of the identical WAS scores. The treatment volume injected during each treatment session for each subject will be recorded in the CRFs.

CaHA: up to two treatment sessions at 4-week interval with the required first treatment at Visit 1 and an optional second treatment at Visit 3 to achieve an optimal cosmetic correction. Each treatment session will be consisted of multiple subdermal injections, up to 1.5 mL/session (or up to 0.75 mL/NLF/session), into the left and right NLFs of each subject according to the IFU. The second treatment is optional and will be determined based on the Investigator assessment. If the subject needs a second treatment, an appropriate amount will be determined at the Investigator discretion to achieve an optimal outcome. The amount of each treatment needs to be equal at the left and right NLFs because of the identical WAS scores. The treatment volume injected during each treatment session for each subject will be recorded in the CRFs.

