10.1 Wrinkle Assessment Scale

Clinical grading of NLF will be performed at baseline for screening purpose. The grading will be based on a 6-point Wrinkle Assessment Scale⁶ according to the numerical definitions (describe in Figure 1 below).

- 0 = no visible, minimal wrinkles
- 1 = just perceptible wrinkles
- 2 = shallow, visible wrinkles with a slight indentation
- 3 = moderately deep wrinkles
- 4 = deep wrinkles, well-defined folds
- 5 = very deep wrinkles, redundant folds

[figure not shown]

Figure 1. Wrinkle Assessment Scale of nasolabial folds

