11. STATISTICAL ANALYSIS

Data of completing subjects will be included for all statistical analyses. Descriptive statistical summary will be performed including N, mean, median, standard deviations, minimum, and maximum of values at all applicable time points and for both treatments.

Comparison between the study treatments will be made in terms of changes from baseline. The null hypothesis, that the mean change from baseline is equal between the 2 study treatments at post-baseline time point, will be tested using methods described in the Statistical Analysis Plan table.

Protocol Version: 04

This document contains confidential, proprietary information.

Statistical Analysis Plan

Evaluation	Change from Baseline	Comparisons between study treatments	Notes/Interpretation
Volume change by 3D imaging analysis	Paired t-test; If normality fails, a Wilcoxon signed-rank test will be used.	Wilcoxon rank-sum test or sample t-test	A higher value reflects an improvement in skin volume.

Statistical analysis for gene expression will be determined using the relative quantification method.

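### The between-product test of nasolabial fold volume change is valid but unadjusted; pre-specifying baseline wrinkle grade (WAS) as a covariate would correct chance imbalance and may add precision

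*Combined protocol and SAP*

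**What the plan says.** Volume is the secondary endpoint: "The secondary objective of this study is to assess and compare volume change in the NLF via clinical photography" (section 5.1). Section 11 sets the scale, "Comparison between the study treatments will be made in terms of changes from baseline", and the table there gives the between-product method as "Wilcoxon rank-sum test or sample t-test". No covariate or model is named. The analysis set is completers: "Data of completing subjects will be included for all statistical analyses".

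On WAS, section 10.1 says: "Clinical grading of NLF will be performed at baseline for screening purpose". Section 6.3 requires at least a shallow fold, so grades 2 to 5 on the 0–5 scale can enter, and requires the same grade on both sides. Section 9.1.1 places eligibility screening before assignment, so each subject has one pre-randomisation value. Section 7.5 describes a list that allocates product and biopsy side; no stratification by WAS is described.

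On the amount injected, section 7.6 says for PLLA: "The treatment amount for each PLLA subject will be determined at the Investigator discretion to achieve an optimal correction". Both products have a per-session maximum, and left and right amounts must match, for which the section gives the equal WAS scores as the reason.

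On size, the synopsis plans "20 subjects to complete (10 subjects per treatment product group"; section 6.1 says only "to achieve maximum 20 subjects who complete the study as planned".

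**The concern.** Fold depth at baseline is a natural candidate predictor of volume change when product is given until correction looks optimal: a deeper fold leaves more to fill. The protocol treats WAS as relevant to amount to the extent that it uses equal grades to justify equal amounts on the two sides. Yet after screening the grade plays no part in the allocation or the analysis.

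Two things are at stake in a trial of 20. If one arm happens to have deeper folds, the unadjusted difference mixes product with fold depth, and the only remedy left is an adjustment chosen after the data are seen. And if WAS does explain part of the variation in volume change, that part stays in the error term of a comparison that can detect only very large differences.

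**Working it through.** **The plan's own figure.** The target of 20 completers cannot be reproduced, because no significance level, power, SD or target difference is stated. The benchmark below is therefore assumed: two-sided 5%, 80% power, differences in units of the within-arm SD of volume change.

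**Inputs.** From the documents: n = 10 per arm (synopsis), unadjusted two-sample test (section 11), eligible WAS 2–5 (sections 6.3 and 10.1). Assumed: r, the within-arm correlation of WAS with volume change, from 0 to 0.7, and a common linear slope in both arms.

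**1. Unadjusted comparison.** The standard error of the difference is √(2/10) = 0.447 SD. With the noncentral t on 18 df, 80% power needs a true difference of 1.32 SD. Power at 1.0 SD is 56%.

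**2. Chance imbalance.** The standardised difference in mean WAS is approximately normal with SD √(2/10) = 0.447.
- More than 0.5 SD: 2 × [1 − Φ(0.5/0.447)] = 0.264, or 26%
- More than 0.75 SD: 9%
- More than 1.0 SD: 2.5%

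An imbalance of 0.5 SD shifts the unadjusted estimate by 0.5 × r: 0.15 SD at r = 0.3, 0.25 SD at r = 0.5 and 0.35 SD at r = 0.7. At r = 0.5 that is 0.25/0.447 = 0.56 standard errors.

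**3. Adjusted comparison.** A linear model with product and WAS has 17 residual df. The variance of the treatment effect relative to the unadjusted analysis is (1 − r²) × [1 + 1/(20 − 4)] = (1 − r²) × 1.0625. The second factor is the expected price of estimating the slope.

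| r | Relative variance | Detectable difference at 80% power (SD) | Power at 1.32 SD, formula | Power at 1.32 SD, simulation |
|---|---|---|---|---|
| unadjusted | 1.00 | 1.32 | 80% | 79–81% |
| 0 | 1.06 | 1.37 | 77.3% | 77.1% |
| 0.3 | 0.97 | 1.31 | 81.0% | 81.5–81.9% |
| 0.5 | 0.80 | 1.19 | 87.8% | 87.4–87.6% |
| 0.7 | 0.54 | 0.98 | 96.6% | 96.9–97.0% |

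Example at r = 0.5: (1 − 0.25) × 1.0625 = 0.797. The simulation used 5,000 trials per setting and two assumed WAS distributions over grades 2 to 5 (30/40/20/10% and 50/40/10/0%).

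**4. Break-even.** (1 − r²) × 1.0625 = 1 gives r = √(1 − 1/1.0625) = 0.24 on variance. Allowing for the t quantile on 17 rather than 18 df, it is 0.26 on interval width.

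**5. Validity.** Under no difference, simulated rejection rates were 4.9–5.6% for the t-test and 4.7–5.5% for the adjusted model. Both hold the 5% level over repeated randomisations.

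**The case against.** The strongest reply is that the gain rests on a correlation nobody has stated.

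- **Link to amount.** A reader might infer that WAS drives how much product each subject receives. Section 7.6 does not say so. It leaves the amount to capped investigator discretion, and cites WAS only to explain why the two sides of one subject are treated equally. That more product means more volume at Day 84 is a further assumption. This stands: prognostic value is plausible, not documented.
- **Precision.** A reader might also infer that precision is certainly being lost. Below r of about 0.25 adjustment costs a little instead. Entry requires a minimum grade and a judgement that only two treatments are needed, which may narrow the spread of WAS and weaken the correlation. This stands as well.
- **Common slope.** The per-fold session limits differ six-fold (4.5 mL against 0.75 mL), so one slope may fit poorly. With r = 0.5 in one arm, 0 in the other and equal outcome SDs, the pooled r is about 0.25 and the relative variance (1 − 0.0625) × 1.0625 = 0.996: no gain, but no loss worth mentioning.
- **Validity.** Chance imbalance is not bias over repeated randomisations, and the standard error already allows for it. The 26% would apply to any unstratified covariate. Both points are correct. What remains is that WAS is the baseline measure of the feature being treated, and that an imbalance seen in the one trial actually run is better handled by a rule fixed beforehand than by a post hoc adjustment.

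**Conclusion.** The concern holds as a cheap improvement to a secondary endpoint, not as an error in the plan. The unadjusted test is valid; a reading that it is biased or inflates the type I error is not supported.

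The plan leaves uncorrected a chance imbalance in fold depth that exceeds 0.5 SD in about one trial in four, and it may forgo precision. The pay-off is asymmetric under the assumed correlations: at worst about 3 points of power lost (80% to 77% at r = 0), against about 7 to 8 points gained at r = 0.5 and 16 to 17 at r = 0.7. Around r = 0.25 it makes no difference.

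These sizes rest on 10 completers per arm, a two-sided 5% level, a linear WAS effect common to both arms, and a benchmark difference of 1.32 SD that is chosen here because the protocol gives none. The imbalance probability needs only the sample size, unstratified allocation and the normal approximation; the shift it causes depends on r.

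**What to change.** In the section 11 table, replace the between-treatment entry for volume with one pre-specified linear model. The outcome is Day 84 change in volume, averaged over the two folds so that there is one value per subject; product is a factor and baseline WAS a single numeric covariate. Keep the unadjusted rank-sum test as a named sensitivity analysis. This also removes the open choice between two tests in that cell.

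Two details go with it. WAS has no row of its own in the section 9 flow chart, so state that the grade is recorded in the CRF as an analysis variable. And do not adjust for the amount injected: it is decided after randomisation and its range differs by product, so it could absorb part of the effect being estimated.

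The cost is a few lines of text, one residual degree of freedom (18 to 17) and up to about 3 points of power if WAS proves unrelated to volume change. No new assessment is needed.

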12. ADVERSE EVENTS

Throughout the course of the study, all adverse events will be monitored and reported on an adverse event CRF/eCRF without omitting any requested and known information. When AEs occur, the main concern is the safety of the study subjects. At time of the informed consent signature, each subject must be given the name and phone number of investigational site personnel for reporting AEs and medical emergencies.

At each visit, after the subject has had the opportunity to spontaneously mention any problems, the Investigator should inquire about AEs by asking the standard questions:

- “Have you had any health problems since your last study visit?”
- “Have there been any changes in the medicines you take since your last study visit?”

AEs should be reported for any clinically relevant change, as determined by the Investigator, in concomitant medication(s) that is the result of an untoward (unfavorable and unintended) change from baseline in a subject’s medical health following exposure to the study treatment.

Changes from baseline in any protocol-specific parameter evaluated during the study are to be reviewed by the Investigator. In addition, the subject’s responses to any questionnaire utilized during the study are to be reviewed by the Investigator. Any untoward (unfavorable and unintended) change from baseline in a protocol-specific parameter or question response that is clinically relevant, in the opinion of the Investigator, is to be reported as an AE. These clinically relevant changes will be reported regardless of causality.

12.1 Definitions

12.1.1. Adverse Events (AE)

An adverse event (AE) is defined as any untoward medical occurrence in a subject taking part in the clinical study, and which does not necessarily require a causal relationship with the investigational product and/or a clinical trial procedure.

An AE can be any unfavourable and unintended sign (including an abnormal laboratory value), symptom, or disease temporally associated with the use of the investigational product, whether or not related to this product.

When an AE has a likely or very likely causal relationship with the investigational product and/or a clinical trial procedure, it is named undesirable effect or related AE (see Section 3).

Protocol GLI.04.US.SL.020

CONFIDENTIAL

12.1.2. Local tolerability signs and symptoms (only applicable for cosmetic safety studies)

In cosmetic studies, local skin tolerability includes some expected functional and/or physical signs on the application area, observed by the Investigator or reported by the subjects. Those signs are collected in the final report based on scales or a diary. If the severity of a local skin tolerability sign or symptom, is such that the product application is permanently discontinued and/or a corrective concomitant treatment (except moisturizer or emollient) is prescribed, it is recorded as an undesirable effect (related AE).

12.1.3. Serious Adverse Events (SAE) and serious undesirable effect/related SAE

A serious adverse event (SAE) involves a serious injury that is life threatening, results in permanent impairment of a body function or permanent damage to a body structure or necessitates medical or surgical intervention to preclude permanent impairment of a body function or permanent damage to a body structure, requires inpatient hospitalization or prolongation of an existing hospitalization.

Notes:

The term "immediate vital risk" refers to an event in which the subject was at risk of death at the time of the event; it does not refer to an event that hypothetically might have caused death if it was more severe.

Inpatient hospitalization is considered to have occurred if the subject has had to stay for a night at the hospital. Hospitalization solely for the purpose of a diagnostic test (even if related to an AE), elective hospitalization for an intervention that was already planned before subject enrolment in the clinical trial, admission to a day-care facility, social admission (e.g., if the subject has no place to sleep), or administrative admission (e.g., for a yearly examination) should not be considered as a SAE.

A serious undesirable effect/related SAE is defined as any SAE which the Investigator classifies as having a reasonable possibility for a causal relationship with the investigational product and/or the clinical trial procedure.

12.2 Severity Assessment

For all AEs occurring during the clinical trial, the Investigator is to classify and report the intensity of AEs using the following definitions as a guideline:

- Mild: awareness of signs and symptoms, but easily tolerated
- Moderate: discomfort, enough to cause interference with usual activity
- Severe: incapacitating, with inability to work or perform usual activity.

12.3 Causality Assessment

The Investigator is to assess the causal relationship (causality) between an adverse event and the investigational product and/or the clinical trial procedure according to the following definitions (Decision of 25 November 2013 on Guideline on Annex I to Regulation (EC) No 1223/2009 (2013/674/EU) - Causality assessment of undesirable effect caused by cosmetic products):

- Very likely
- Likely
- Not clearly attributable

Protocol Version: 04

This document contains confidential, proprietary information.

Protocol GLI.04.US.SL.020

CONFIDENTIAL

- Unlikely
- Excluded

Medical judgment should be used to determine the relationship, considering all relevant factors including the pattern of reaction, temporal relationships, positive de-challenge or re-challenge, relevant medical history, and confounding factors such as co-medication or concurrent diseases.

12.4 Collection, Management and Reporting Procedures

The period of collection of adverse events starts from the time of signature of the Informed Consent Form (ICF) by the subject (*and/or, for subjects who are minor, by the parents/legal representatives*) until the end of the subject's participation in the clinical study.

If a Serious Adverse Event (SAE) is on-going at the final clinical trial visit, it should be followed by the Investigator until it has resolved or has reached a stable condition.

After the subject completes the clinical study, the Investigator should also inform the Sponsor (see Sponsor's contact details below) if he/she becomes aware of an SAE involving a subject who has participated in the clinical study.

At each post-enrollment visit, the Investigator will question the subject about AEs using an open non-persuasive question to elicit reporting of AEs, for example "*Have you noticed any change in your health since the last visit?*" Direct questioning and examination will be performed when appropriate.

The Investigator will obtain and maintain in the subject's files all pertinent medical records, and (if applicable) information and medical judgment from colleagues who assisted in the treatment and follow-up of the subject. If necessary, the Investigator will contact the subject's personal physician or hospital staff to obtain further details.

As a minimum, Investigators are requested to report in the Case Report Form (CRF) and in the report all related adverse events (i.e. undesirable effects) and all Serious Adverse Events, whether related or not.

12.4.1. Management and reporting procedures for undesirable effects (i.e. related adverse events)

Undesirable effects should be recorded in the CRF and summarized in the report in a summary table with at minimum the subject number, AE number, AE diagnosis or signs and symptoms, location, date of onset, seriousness, severity, action taken, relationship, date of resolution and concomitant treatment associated as well as a detailed narrative of the event.

In addition, based on his/her medical judgment, the Investigator will assess whether an undesirable effect requires immediate (i.e. within 24 hours) reporting to the Sponsor. In such cases, the summary table will be sent to the Sponsor, along with the AE narrative and any other relevant information (concomitant treatments, product weighing, ...).

All undesirable effects should be appropriately documented, i.e. any relevant information such as demographics, medical history and concomitant therapies should be recorded in the CRF.

The Investigator is to monitor and record the progress of the adverse effect until the last subject's study visit.

The Investigator is to update the AE narrative as appropriate, each time follow-up information is collected and when the final outcome of the adverse effect is known.

Protocol Version: 04

This document contains confidential, proprietary information.

Protocol GLI.04.US.SL.020

CONFIDENTIAL

12.4.2. Management and reporting procedures for Serious Adverse Events

The Investigator is to take the following steps:

1. Take prompt and appropriate medical action, if necessary. The safety of clinical trial subjects is the first priority
2. Ensure the AE is classified as an SAE. Immediately inform the Sponsor's representative of the event by email or fax (see both contact details below) and discuss further actions to be taken:

Global PV email: [contact]

US PV email: [contact]

3. Complete the Serious Adverse Event (SAE) form provided by the Sponsor's representative **Within 24 hours**, fax or send by e-mail **to the Sponsor's representative** the completed SAE form, accompanied any other relevant information (e.g. test results or medical records).
4. Monitor, record and send to Sponsor's representative the progress of the event until it resolves or reaches a stable outcome, with or without sequelae (send the updated SAE form with follow-up information and any other relevant information to Sponsor's representative).
5. Obtain and maintain in the subject's file all pertinent medical records, information, and medical judgments from colleagues who assisted in the treatment and follow-up of the subject. If necessary, contact the subject's personal physician or hospital staff to obtain further details.
6. If applicable, comply with the regulatory requirement(s) related to the reporting of SAEs to the Institutional Review Board (IRB) / Independent Ethics Committee (IEC).

